### **3.2. Clarification of Hierarchical Testing Strategy**

Section 8.4 of the SAP specifies that all endpoints tested at Year 1 and Year 2 will use a significance level of 0.025. Within each year, endpoints are tested following a fixed-sequence hierarchical testing strategy. The total significance level (0.05) was split between Year 1 and Year 2 as a strategy to reserve alpha to test Year 2 if the Year 1 testing sequence was not statistically significant. Formal testing in the sequence may proceed so long as statistically significant evidence of benefit continues to be shown. If in the sequence one endpoint does not show statistically significant evidence of benefit, formal statistical testing of subsequent endpoints will not occur.

As a clarification to the SAP, if there is a significant treatment effect for both Year 1 endpoints, then the significance level for Year 1 (0.025) remains available to be carried forward (recycled or passed along) to the Year 2 testing sequence. Thus, if both Year 1 endpoints are significant, the Year 2 testing sequence will be tested using a significance level of 0.05. This approach aligns with the fixed-sequence method in FDA guidance (Multiple Endpoints in Clinical Trials., January 2017).

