### 2.1. Trial Rationale

Conceptually, this trial was designed to test the biological hypothesis that bardoxolone methyl slows disease progression in patients with Alport syndrome, as measured by changes in eGFR. Since on-treatment changes in eGFR may include both reversible, pharmacodynamic effects, as well as irreversible structural effects, analysis of eGFR after withdrawal is used to determine if bardoxolone methyl affects disease progression.

The presence of a sustained eGFR improvement after withdrawal of drug may be indicative of disease-modifying activity. In contrast, a decline in kidney function relative to placebo after drug withdrawal would be unlikely to provide a long-term benefit and could indicate the drug has harmed the kidney.

If the withdrawal analysis indicates that bardoxolone methyl improves kidney function relative to placebo, then this would suggest that the drug is likely to reduce underlying progression of the disease. It would also suggest that the on-treatment eGFR change would likely translate into a long-term renal benefit. Further, in routine clinical practice, physicians are unlikely to withdraw the drug, and an important element of the trial is to characterize the on-treatment eGFR change.

Analytically, the main intent of the trial is to characterize the change from baseline in eGFR following a 4-week withdrawal period. Within the two-year duration, there are two opportunities to test this biological hypothesis and determine if the change from baseline in eGFR is statistically significant relative to placebo. If the off-treatment change from baseline in eGFR is not statistically significant relative to placebo at Year 1, the trial design and analysis plan allow for an additional comparison of the off-treatment effect relative to placebo at Year 2.

Beyond the main intent of the trial, the trial is designed to also determine the following:

- The clinical benefit of bardoxolone methyl while receiving treatment, as measured by the on-treatment assessment of eGFR.
- Whether a treatment effect is observed over a period of up to two years.
- Whether a treatment effect trend is seen across various subgroups, such as stages of disease (i.e., across a spectrum of baseline eGFRs) and the pediatric population.

This document describes the analyses of protocol-specified endpoints to assess the effects of bardoxolone methyl on disease progression in patients with Alport syndrome.

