#### 4.3.1. Primary Endpoints

With 157 patients enrolled (78 in one group and 79 in the second group), the study will have approximately 80% power to detect a difference between the two treatment groups in change from baseline in eGFR of 3.4 mL/min/1.73 m^2 for the primary endpoint at Week 48 in Year 1. The power calculation for Year 1, which was based on mixed-model repeated measures (MMRM) analysis, assumes the following:

- 9 repeated measurements (Weeks 1, 2, 4, 6, 8, 12, 24, 36, and 48) having compound symmetry covariance structure
- The correlation between observations on the same subject is 0.7
- Two-sided Type I error rate of 0.025
- Standard deviation of change from baseline in eGFR of 8 mL/min/1.73 m^2
- Analyses at Week 48 are based on the intent-to-treat (ITT) population

Analysis of the Year 2 primary endpoint, which also will use the ITT population, will have approximately 80% power to detect a difference of 3.3 mL/min/1.73 m^2 assuming 13 repeated measurements, a correlation of 0.7 between observations, a standard deviation of 8 mL/min/1.73 m^2, and a two-sided type I error rate of 0.025. The primary analysis of efficacy will use an unstructured covariance structure, which is expected to have approximately the same power as the analysis with compound symmetry used for study planning.

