#### 4.3.2. Key Secondary Endpoint

With 157 patients enrolled, the study will have a minimum detectable difference (i.e., 50% power) between the two treatment groups in change from baseline in eGFR of approximately 2.9 mL/min/1.73 m^2, and 80% power to detect a difference of 4.0 mL/min/1.73 m^2 for the key secondary endpoint at Year 1 and at Year 2. The power calculation, which was based on a 2-sample t-test as an estimate for the planned ANCOVA analysis, assumes the following:

- Two-sided Type I error rate of 0.025 for Year 1 and 0.025 for Year 2
- Standard deviation of change from baseline in eGFR of 8 mL/min/1.73 m^2
- Multiple imputation is used for missing data
- Analyses of the key secondary endpoint are based on the ITT population

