#### **8.4. Multiple Comparisons and Multiplicity**

The trial includes separate Phase 2 and Phase 3 cohorts, where the cohorts constitute independent sets of patients. Therefore, the Phase 2 analysis has no impact on the Type I error rate for the Phase 3 analysis.

The Phase 3 cohort includes a family of hypothesis tests following the first year of treatment and a second family of hypothesis tests following the second year of treatment. All endpoints tested at Year 1 will use a significance level of 0.025 and those tested at Year 2 will also use a significance level of 0.025. Within each year, endpoints are tested following a fixed-sequence hierarchical testing strategy. Formal testing in the sequence may proceed so long as statistically significant evidence of benefit continues to be shown. At such point in the sequence that one endpoint does not show statistically significant evidence of benefit, formal statistical testing of subsequent endpoints will not occur.

Testing endpoints in the following sequence protects the overall type I error rate of 0.05 for the study:

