##### **Year 2 Testing Sequence (all significance levels = 0.025)**

1. eGFR at Week 100 (primary at Year 2)
2. eGFR at Week 104 (key secondary at Year 2)

3. time-to first kidney failure composite (exploratory at Year 2)
4. distribution of PGIC at Week 100
5. distribution of CGI-I at Week 100

All remaining endpoints are considered “Exploratory” and presented with nominal significance levels for descriptive purposes only.

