### **9.4. Kidney Failure Composite Outcome**

#### **9.4.1. Primary Analysis of the Kidney Failure Composite Outcome**

The kidney failure composite outcome is defined as reaching one of the following:

- Confirmed 30% decline from baseline in eGFR; or
- Confirmed eGFR < 15 mL/min/1.73 m^2; or
- ESKD (initiation of maintenance dialysis or kidney transplant).

A 30% decline or eGFR < 15 is considered confirmed when the threshold is achieved at  $\geq 2$  visits. Patients who achieved the threshold at their last visit, and did not have a second confirmatory visit, are considered confirmed. The analysis uses initiation of maintenance dialysis or kidney transplant as reported in the database by the investigator. Patients with a decrease from baseline in eGFR of 30% or more at the last on-treatment visit are considered to have a 30% or more decrease from baseline eGFR. In the event a patient has both an increase from baseline in eGFR of 30% or more and a decrease from baseline in eGFR of 30% or more, only the decrease from baseline is considered in composite endpoint analyses. Confirmation of kidney failure components is based on all on-treatment eGFR values, irrespective of analysis windows. The date of the first eGFR meeting the kidney failure component is used in time-to-event analyses as the date of the event.

For the Year 1 analysis, the number and percentage of patients in each treatment group having a kidney failure composite by Week 52 are summarized using only on-treatment eGFR values. The proportion of patients with a given event is evaluated using Newcombe’s test accounting for ACR\_STRAT. Similarly, the number and percentage of patients in each treatment group having a kidney failure composite by Week 104 are summarized for the Year 2 analysis.

For the Year 2 endpoint (Section 3.1.2.3), a time-to-event analysis of the kidney failure composite is performed using only on-treatment eGFR values. Missing eGFR data are not

imputed for time-to-event analyses. Hazard ratios and 95% CIs are computed using Cox proportional hazards regression models. Patients who do not experience a confirmed event are censored for time-to-event analysis using the following conventions:

- patients who died from any cause prior to the end of the study are censored at the date of death;
- patients who discontinued the study prematurely, withdrew consent, or were lost to follow-up prior to the end of the study are censored at their last date of contact;

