#### **9.4.2. Sensitivity Analysis**

The primary time-to-event analysis described in Section 9.4.1 is repeated as a sensitivity analysis with all-cause death added to the kidney failure composite.

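### The kidney failure composite reads its eGFR components only on treatment against a pre-drug baseline, so a reversible rise on drug can make the reported effect overstate any effect on progression

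*SAP*

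**What the plan says.** **Endpoint.** SAP section 9.4.1 defines the composite as a confirmed 30% fall in eGFR from baseline, a confirmed eGFR below 15, or ESKD (maintenance dialysis or transplant). For Year 2, "a time-to-event analysis of the kidney failure composite is performed using only on-treatment eGFR values". Confirmation also uses on-treatment values only, and so do the percentages with an event by Week 52 and, by analogy, by Week 104.

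**Baseline.** SAP section 6.4.1 averages the screening eGFR with the Day 1 value taken before the first dose, so baseline is free of drug.

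**Rationale.** SAP section 2.1 begins its case for the withdrawal design: "Since on-treatment changes in eGFR may include both reversible, pharmacodynamic effects, as well as irreversible structural effects". It goes on to use eGFR after withdrawal to decide whether the drug affects progression.

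**Place in the testing.** The composite is called exploratory but stands third in the Year 2 sequence of SAP section 8.4, after eGFR at Week 100 and off-treatment eGFR at Week 104. Testing stops at the first endpoint that fails. By default, endpoints "those tested at Year 2 will also use a significance level of 0.025". Under section 3.2 of the SAP addendum, if both Year 1 endpoints succeed, "the Year 2 testing sequence will be tested using a significance level of 0.05".

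**Sensitivity analysis.** The only one, in SAP section 9.4.2, says that the analysis "is repeated as a sensitivity analysis with all-cause death added to the kidney failure composite".

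**The concern.** The composite uses the measurements that section 2.1 calls ambiguous and leaves out the off-treatment values that the trial collects to resolve the ambiguity. If part of the on-drug eGFR is a reversible rise, a drug patient must lose more underlying function than a placebo patient before the same event is recorded. The arms can then differ in events while progressing identically.

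This does not depend on patients stopping drug early; it is present if everyone takes drug to Week 100. Adding death to the composite leaves it untouched. At stake is how the hazard ratio, its interval and the percentages are read. Under a kidney failure label they will be taken as prevention of progression, and nothing planned for this endpoint lets a reader separate that from a reversible rise.

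**Working it through.** **1. The plan's own figures.** The documents give no event rate, hazard ratio or power for the composite. The nearest stated figures are those of SAP sections 4.3.1 and 4.3.2: 78 and 79 patients, SD of change 8, and, for the key secondary endpoint, "Two-sided Type I error rate of 0.025 for Year 1 and 0.025 for Year 2".
- SE = 8 × √(1/78 + 1/79) = 1.277.
- Detectable difference at 50% power = 2.241 × 1.277 = 2.86 (SAP: about 2.9).
- Power at 4.0 = Φ(4.0/1.277 − 2.241) = 81.4%, or 80.7% by noncentral t (SAP: 80%).
- Week 48, 9 visits, correlation 0.7: SD factor √[(1 + 8 × 0.7)/9] = 0.856, SE 1.094, power at 3.4 = 80.7% (SAP: about 80%).
- Week 100, 13 visits: SD factor 0.850, SE 1.086, power at 3.3 = 78.7% (SAP: about 80%).

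These inputs reproduce, so they are used below.

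**2. Threshold arithmetic.** With baseline B and a reversible rise r, a placebo patient meets the 30% criterion after an underlying fall of 0.3B, a drug patient after 0.3B + r.

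| Baseline | Placebo | Drug, r = 1.7 | Drug, r = 3.4 |
|---|---|---|---|
| 60 | 18 (30%) | 19.7 (32.8%) | 21.4 (35.7%) |
| 30 | 9 (30%) | 10.7 (35.7%) | 12.4 (41.3%) |

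Likewise, the eGFR < 15 criterion requires underlying eGFR below 13.3 or 11.6 in the drug arm. The direction needs no simulation.

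**3. Size by simulation, with identical progression in both arms.**
- From the SAP: 78 and 79 patients, 13 on-treatment visits, SD of change 8, correlation 0.7, and the confirmation rule of 9.4.1 (two or more visits, or the last visit).
- Assumed: baseline uniform over 30 to 90 (the eligibility range), slope −2 to −6 mL/min/1.73 m² per year, full adherence, no ESKD events, and the same additive rise in every drug patient, at plateau by Week 8. A log-rank test stands in for the Cox test.
- The rise of 3.4 is the whole Week 48 difference that the SAP powers for, taken as fully reversible; 1.7 is half of it.

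| Reversible rise | Hazard ratio | Rejects, two-sided 0.025 | Rejects, two-sided 0.05 |
|---|---|---|---|
| 1.7 | about 0.75 | 4–8% | 8–13% |
| 3.4 | 0.51–0.57 | 13–28% | 19–40% |

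The ranges run over the slopes, and the rates ignore the gate. With no rise the test rejects in 4–6% at 0.05 and the hazard ratio is about 1. At slope −4 and rise 3.4 there are about 14 placebo and 8 drug events.

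A second model (random slopes, within-patient SD 5) agrees: at slope −4, a rise of 3.3 gives 16.9% against 8.6% with an event and a hazard ratio of 0.48. In that model a rise of 4.0 gives 0.41, which becomes 0.44 with within-patient SD 3 and 0.56 with SD of change 12.

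**4. The gate.** If no drug effect remains at Week 104, that test favours drug with probability α/2: 1.25% at two-sided 0.025 and 2.5% at 0.05. A formal composite claim cannot be more frequent. The simulated ceilings, about 1.4% and about 3%, agree within simulation error.

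**5. After the gate.** With a real benefit of 1.5 per year (about 1.5 × 700/365.25 = 2.9 by Week 100), adding a reversible 4.0 moves the hazard ratio from 0.60 to 0.26. With a durable 4.0, adding a reversible 3.4 moves it from 0.61 to 0.30. These are large combined on-drug effects (about 6.9 and 7.4); they show direction, not an expected size.

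**6. Off-treatment reading.** In simulation, the same thresholds applied to Week 52 and Week 104 off-treatment eGFR reject in 4–6% at two-sided 0.05 when progression is identical.

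**The case against.** **The gate already does this job.** A reader might infer that the plan permits a false formal claim of kidney protection at the rates in step 3. It does not. The composite is formally tested only after off-treatment Week 104 eGFR succeeds, and the default level is 0.025, with 0.05 only if both Year 1 endpoints succeed. This stands and limits the point to estimation and interpretation. But 9.4.1 specifies the hazard ratio and interval without reference to the gate, and the Year 1 percentages are in no testing sequence.

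**The rise is assumed.** Section 2.1 says only that on-treatment changes may include reversible effects. A rise of the same amount in every patient is a modelling device, and treating the full 3.4 as reversible is a strong case. Halving it leaves a much smaller distortion. This stands, and is why a range is shown.

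**On-treatment benefit is a declared aim.** Section 2.1 notes that physicians are unlikely to withdraw the drug, and 9.4.1 is open about which values it uses. So the analysis should stay; what it lacks is an accurate description and an off-treatment companion.

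**Off-treatment eGFR is reported elsewhere.** The Week 52 and Week 104 analyses of covariance, their sensitivity analyses and the distribution plots will show whether mean differences persist. None of them shows how many patients in each arm cross the composite's thresholds off drug.

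**Conclusion.** The point holds as one of estimation and interpretation. A reversible rise on drug, if there is one, lowers the drug arm's event rate, and the reported hazard ratio, interval and percentages can then overstate an effect on progression. With equal progression and the assumptions above, the hazard ratio would be about 0.75 for a rise of 1.7 and 0.51 to 0.57 for a rise of 3.4. The direction follows from the definitions; the size depends on the rise, slope and baseline distribution, none of which the documents give. ESKD events are not derived from eGFR and would dilute the distortion if common; no expected number is stated.

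The documents do not support the stronger conclusions that Type I error control fails, that the composite measures nothing but on-drug eGFR level, or that a reversible effect of any particular size exists. This is an inexpensive improvement to an exploratory, gated endpoint, not a flaw in the primary or key secondary analyses.

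**What to change.** **SAP section 9.4.2.** Add a sensitivity analysis of the composite with the eGFR components read at the Week 52 and Week 104 off-treatment assessments. A single off-treatment value at or beyond the threshold (30% fall from baseline, or eGFR below 15) counts, and ESKD counts as now. Report the proportion by arm, with a difference and confidence interval stratified by ACR_STRAT, beside the 9.4.1 result.

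**Missing Week 104.** Patients not dispensed drug in Year 2 have Week 104 missing by definition (SAP Table 3, note g; addendum Table 4, note a). State how they are handled, for example by using their Week 52 off-treatment value.

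**SAP section 9.4.1.** Describe the present result as an on-treatment eGFR composite.

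Do not make a claim depend on the two versions agreeing in approximate size. No margin is available, and about 14 against 8 events could not support the judgement.

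**Cost.** SAP wording and one table from data already collected. With only two off-treatment time points, timing is coarse and precision lower. Without confirmation, single values also admit more measurement noise, so the new proportions should be compared between arms, not with the level of the 9.4.1 rates.

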#### **9.4.2. Sensitivity Analysis**

The primary time-to-event analysis described in Section 9.4.1 is repeated as a sensitivity analysis with all-cause death added to the kidney failure composite.

## 10. SAFETY AND TOLERABILITY

Safety and tolerability are evaluated by AEs, SAEs, clinical laboratory test results, body weight, vital signs, 12-lead ECG findings, physical examination, visual acuity, and audiology assessment. All analyses of the safety data are performed using the safety analysis set.

Descriptive statistics are presented by treatment group assignment in the safety analysis set. No formal statistical testing is performed for safety analyses. Safety is also summarized by the subgroups defined in Section 8.3. On-treatment values are summarized according to the analysis study windows in Section 6.5.4; off-treatment values are summarized according to the analysis study windows in Section 6.5.4.1. Safety data summaries are grouped by treatment year.

Continuous safety parameters (including selected clinical chemistries and vital signs) may be summarized using the methodology described in Section 8.6.1, Section 8.7.1, Section 8.8.1, and Section 8.9.1. Only the visit windows outlined in Table 3 are included in these analyses.

### 10.1. Adverse Event Preferred Term and Body/Organ System Summary Tables

AEs are summarized by treatment as defined by the safety analysis set. In addition to being summarized by treatment year, AEs are also summarized overall. General considerations for AE summaries and calculations are:

- Multiple events by preferred term (PT) and system organ class (SOC) are counted once only per patient for summaries of AE incidence.
- For summaries of AE incidence by severity, only the most severe event is counted per patient.
- For summaries of AE incidence by relationship, only the most related event is counted per patient.
- An AE with a missing resolution date or incomplete date that is not identified as continuing is assumed to be continuing and no duration is calculated.
- Treatment-emergent adverse events (TEAEs) are summarized separately from off-treatment adverse events (OTAEs).
- For summaries of the number of AE events, all AEs are counted.

AEs are coded using MedDRA (Medical Dictionary for Regulatory Activities) version 19.1. In MedDRA, each verbatim term is mapped to a preferred term and high level term (HLT), which is then mapped to a system organ class. Tables and listings will present data at the SOC and PT level.

Treatment-emergent adverse events (TEAEs) are events that either:

- Have a date of onset on or after the date of the date of first dose and not more than 30 days after the date of the last dose of study drug, or
- Have no recorded date of onset with a stop date after the first dose of study drug, or
- Have no recorded date of onset or stop date

AEs with an onset greater than 30 days after the last dose of study drug, and therefore not treatment-emergent AEs (TEAEs), are classified as off-treatment AEs (OTAEs). Analyses described for TEAEs are also performed for OTAEs and tabulated separately.

The investigator grades the severity of the AEs as mild, moderate, or severe as defined in the study protocol. The investigators graded association or relatedness to the study medication according to criteria specified in Section 11.4 of the study protocol.

As defined in the protocol, a serious adverse event (SAE) is an adverse event that results in any of the following:

- Death;
- A life-threatening adverse drug experience;
- Inpatient hospitalization or prolongation of existing hospitalization;
- Results in persistent or significant incapacity or substantial disruption of the ability to conduct normal life functions;
- Results in a congenital anomaly or birth defect in an offspring of a patient taking study drug;
- Is an important medical event.

#### **10.1.1. Missing and Partial AE Onset Dates**

Rules for handling missing or partial AE Onset Dates are included in Section 6.6.3.

#### **10.1.2. Summaries of Adverse Events**

TEAEs and OTAEs are summarized by treatment based on year of AE onset, and overall. For each treatment, SOC, and PT, the number and percentage of patients reporting an event is calculated. In summary tables, SOC is presented alphabetically and events within SOC are presented by decreasing frequency count.

Summary tables (number and percentage of patients and events) of AEs (by SOC and PT) are provided by treatment as follows:

- All treatment-emergent AEs
- All treatment-emergent related AEs (definitely, probably, or possibly related)
- All treatment-emergent AEs by severity
- All treatment-emergent serious adverse events (including deaths)
- All related treatment-emergent serious adverse events (including deaths)
- All treatment-emergent adverse events leading to permanent discontinuation of study drug

Listings are provided showing:

- All AEs
- Serious adverse events (including deaths)

- AEs leading to permanent discontinuation of study drug

